#### **9.6.3            Vital Signs**

The actual value, change and percent change from baseline in vital signs will be summarized over time by treatment arm for systolic blood pressure, diastolic blood pressure, heart rate, respiratory rate, and temperature.

#### **9.6.4            Physical Measurements**

The actual value, change and percent change from baseline in weight and BMI will be summarized by treatment arm and by scheduled visit.

#### **9.6.5            Electrocardiogram**

The ECG (Electrocardiogram) measurements from this clinical study were performed as per standard of care for routine safety monitoring, rather than for purposes of assessment of potential QTc (corrected QT Interval) effect. Since these evaluations may not necessarily be performed under the rigorous conditions expected to lead to meaningful evaluation of QTc data; summaries and statistical analyses of ECG measurements are not planned, and these data would not be expected to be useful for meta-analysis with data from other trials.

#### **9.6.6            Antibody Formation**

The incidence and percentage of subjects who develop anti-efavaleukin alfa antibodies and cross reactive anti-IL-2 antibodies (binding and if positive, neutralizing) will be summarized by treatment group. Furthermore, the incidence and percentage of subjects with treatment-boosted anti-efavaleukin alfa antibodies will also be summarized.

In addition, subjects with positive binding and neutralizing anti-efavaleukin alfa results will be listed individually with corresponding time points.

#### **9.6.7            Exposure to Investigational Product**

Descriptive statistics will be produced to describe the exposure to IP by treatment arm and by study period and overall. Summary statistics will be provided for the total number of doses administered, total dose received, and total duration of IP exposure by treatment arm and by study period and overall.

#### **9.6.8            Exposure to Other Protocol-permitted Therapy**

Protocol-permitted therapy includes oral 5-ASA compounds, immunomodulators, and oral corticosteroids.

Descriptive statistics of number and percentage of subjects with dose modifications, including steroid tapering of corticosteroids in the long-term treatment period, will be produced by treatment arm.

The number and percentage of subjects taking oral 5-ASA compounds, immunomodulators, and oral corticosteroids will be provided.

#### **9.6.9        Exposure to Concomitant Medication**

Not applicable

#### **9.7        Other Analysis**

Not applicable

#### **9.7.1        Analyses of Clinical Outcome Assessments**

Not applicable

#### **9.7.2        Analyses of Health Economic Endpoints**

Not applicable

### **10.        Analyses of Biomarker endpoints**

Not applicable

### **11.        Changes From Protocol-specified Analyses**

- The third interim analysis conducted for the study in August 2024 revealed that the study met futility criteria, leading to its termination. As a result of this decision, select exploratory endpoints originally included in the Statistical Analysis Plan (SAP) are being removed. These endpoints will not be discarded entirely; instead, they will be documented in a Supplemental Statistical Analysis Plan (SSAP) and will not be documented in CSR.
- Subject data from site 66164 are not included in the analysis set because the site closed due to noncompliance with the protocol and FDA regulations. The following listings for the affected subjects will be generated separately:
  - Adverse Events
  - Concomitant Medications
  - Laboratory Data

**13. Appendices**

**Appendix A. Reference Values/Toxicity Grades**

Assessment of severity for each adverse event and serious adverse event reported during the study will be based on:

The Common Terminology Criteria for Adverse Events (CTCAE), version 5 which is available at the following location:

[http://ctep.cancer.gov/protocolDevelopment/electronic\\_applications/ctc.htm](http://ctep.cancer.gov/protocolDevelopment/electronic_applications/ctc.htm)

### Appendix B. Analytical Windows

Since the actual visit for a subject may not exactly coincide with their scheduled visit date, to allow for variations in scheduling, the following visit windows will be used to assign evaluations to a most appropriate nominal visit for analysis and summarization. Furthermore, there will be no gaps between visit windows in order to include as many data points as possible for summarization.

If more than one actual visit (including the unscheduled visits) falls within the same defined window, the visit closest to the target day with non-missing data will be considered for analysis. If two actual visit dates are at the same distance from the target day, the latest visit with non-missing data will be considered for analysis.

If more than one evaluation falls on the same date and time for laboratory results, then the value with the smallest accession number will be used.

Analysis visit windows for selected assessments are included in tables below. For remaining assessments, no visit window will be applied.

Study Day Window				
Analysis Visit	Target Day	Vital Signs	Chemistry, Hematology, Urinalysis	Fecal Calprotectin, hsCRP
6 to 24 hour Post Dose	1	1-2		
48 to 96 hour Post Dose	3	3 - 5		
		6 - 19	2 - 22 (Chemistry and Hematology only)	
		20 - 26		
		27 - 35	23 - 42 (Chemistry and Hematology) 2 - 42 (Urinalysis)	2 - 42
		36 - 49		
		50 - 63	43 - 70	43 - 70
		64 - 77		

	78 - end of induction date	71 - end of induction date	71 - end of induction date
	(end of induction date + 1) - 105		
106 - 119		(end of induction date + 1) - 126	
120 - 133			
134 - 147		127 - 154	
148 - 161			
162 - 175		155-182	(end of induction date + 1) - 210 (Fecal Calprotectin only)
176 - 189			
190 - 203		183-210	
204 - 217			
218 - 231		211-238	
232 - 245			
246 - 259		239-266	211 - 308 (Fecal Calprotectin only)
260 - 273			
274 - 287			
288 - 301			
302 - 315			
316 - 329			
330 - 343			

	344 - 357		
	358 - 378	267-378	309 - 378 (Fecal Calprotectin only)

Analysis Visit	Target Day	Study Day Window			
		Anti-efavaleukin alfa antibody	Partial Mayo Score, Physician Global Assesment (PGA)	Lymphocyte subset	Weight, Modified Mayo Score, endoscopy and Geboes score
	2 - 22	2 - 19	2 - 19		
		20 - 26	20 - 26		
	23 - 42	27 - 35			
		36 - 49	27 - 49		
	43 - 70	50 - 63			
		64 - 77			
	71 - end of induction date	78 - end of induction date	50 - end of induction date	2 - end of induction date	
		(end of induction date + 1) - 126			
		127 - 154			

	(end of induction date + 1) - 210	155 - 182	(end of induction date + 1) - 210	
		183 - 210		
		211 - 238		
211 - 308	239 - 266	211 - 308		
	267 - 294			
	295 - 322			
	323 - 350			
309 - 378	351 - 378	309 - 378	(end of induction date + 1) - 378	

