Pregnancy Test ^d		Urine		Urine		Urine		Urine		Urine		Urine		Urine		Urine		Urine		Urine
Hematology	X		X		X		X		X		X		X		X					X
Chemistry	X		X		X		X		X		X		X		X					X
Urinalysis	X		X		X		X		X		X		X		X					X
Fecal Calprotectin					X								X							X
IMMUNOGENICITY ASSESSMENTS																				
Anti-efavaleukin alfa antibody						X							X							X
BIOMARKER ASSESSMENTS^{b,g}																				
Biomarker Development Sample						X							X							X
Lymphocyte Subset						X							X							X
Biomarker Mucosal Biopsy Sample																				X
EFFICACY ASSESSMENTS																				
Partial Mayo Score Review		X		X		X		X		X		X		X		X		X		X
Endoscopy																				X ^a
Mucosal Biopsy (histopathology)																				X

Page 1 of 2

Footnotes defined on the last page of the table.

Table 1-3. Schedule of Activities – Exploratory Long-term Treatment Period

WEEK	Long-term Treatment Period																			W52/ ET ^a
	STUDY DAY ± VISIT	± 5	± 5	± 5	± 5	± 5	± 5	± 5	± 5	± 5	± 5	± 5	± 5	± 5	± 5	± 5	± 5	± 5	± 5	
CLINICAL OUTCOME ASSESSMENTS																				
Physician Global Assessment		X		X		X		X		X		X		X		X		X		
Mayo Daily Symptom Diary (daily)																				
IBDQ																				X
PGIS																				X
PGIC																				X
EQ-5D-5L																				X
STUDY TREATMENT																				
Investigational Product Administration ^e																				

Page 2 of 2
 ECG = electrocardiogram; ET = Early termination visit; EQ-5D-5L = EuroQol-5-Dimension 5 levels; hsCRP = high sensitivity C-reactive protein; IBDQ = inflammatory bowel disease questionnaire; PGIC = Patient Global Impression of Change; PGIS = Patient Global Impression of Severity; UC = ulcerative colitis; [REDACTED]

^a An ET is required for all subjects who discontinue the study completely prior to week 52. If a subject undergoes early termination soon after having their screening or week 12 endoscopy, the need for an ET endoscopy should be discussed with the Amgen physician.

^b If permitted by local regulations, the investigator may utilize a qualified home health care service provider, approved by sponsor, for collection of PK, biomarker samples, and ECG on visits without a scheduled administration of investigational product (See Section 6.1.4.1).

^c After end of study, serious adverse events suspected to be related to investigational product will be reported to Amgen. Please refer to Section 8.4.4.1.3 for additional details.

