#### **9.6.2            Laboratory Test Results**

Change and percent change from baseline in select clinical laboratory test results will be summarized over time by each treatment group. In addition, shift tables, from baseline to the worst on-study laboratory toxicity based on the CTCAE version 5 or later will be presented.

Subject incidence of worst post-baseline of eosinophils counts and percentages by the laboratory normal range will be tabulated by treatment group.

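### SAP Appendix B puts laboratory days 267 to 378 into one final window that fits no plausible visit schedule, so late panels can be dropped from, or mislabelled in, the by-visit laboratory summaries

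*SAP*

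**What the plan says.** SAP Appendix B assigns each evaluation to a nominal visit by study day: "the following visit windows will be used to assign evaluations to a most appropriate nominal visit for analysis and summarization". It states two general rules. The first is that "there will be no gaps between visit windows in order to include as many data points as possible for summarization". The second, for several visits in one window, is that "the visit closest to the target day with non-missing data will be considered for analysis".

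After induction, chemistry, hematology and urinalysis share seven windows: end of induction + 1 to 126, 127–154, 155–182, 183–210, 211–238, 239–266 and 267–378. The last is on the row where vital signs have 358–378, which is week 52.

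Other columns treat the same days differently:

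- Partial Mayo also has 239–266, then 267–294, 295–322, 323–350 and 351–378.
- Fecal calprotectin has 211–308 and then "309 - 378 (Fecal Calprotectin only". Antibody and lymphocyte subsets have the same day ranges.

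Protocol Table 1-3 (Section 1.3) lists the long-term samples. The hematology row reads "Hematology X X X X X X X X X", which is nine marks. The chemistry and urinalysis rows match it.

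The windows feed SAP Section 9.6.2: "Change and percent change from baseline in select clinical laboratory test results will be summarized over time by each treatment group". The same section plans shift tables "from baseline to the worst on-study laboratory toxicity based on the CTCAE version 5 or later will be presented".

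**The concern.** The step from 28-day windows to one of 112 days looks like an omission or a misplaced boundary. Closing a window at day 266 implies a further laboratory visit about four weeks after the one it belongs to, yet no window is provided for such a visit.

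Two things would follow. A subject with a week 52 sample would lose any earlier scheduled panel taken on or after day 267 from the by-visit tables, which works against the appendix's aim of using as many data points as possible. A subject without a week 52 sample would have the latest panel in the window shown as week 52, however early it was taken. The week 52 laboratory summary could then mix values from about week 38 (day 267) to week 54 (day 378).

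**Working it through.** **Inputs.** Protocol Table 1-2 puts week 12 at day 85 and Table 1-3 puts week 52 at day 365, both ± 5 days. Both fit day = 7 × week + 1. The other week numbers and the long-term target days are not visible, so weeks 36, 40, 44 and 48 below are inferred as days 253, 281, 309 and 337.

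**Step 1: reproduce the other columns.** Let each later window open at the midpoint of adjacent targets, (t₁ + t₂)/2. Take the opening at end of induction + 1 and the final limit of 378 as given.

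- Vital signs, every 2 weeks: weeks 50/52 give (351 + 365)/2 = 358. All 20 long-term windows are reproduced.
- Partial Mayo, every 4 weeks: weeks 36/40 give (253 + 281)/2 = 267. All 10 are reproduced.
- Fecal calprotectin at weeks 24, 36 and 52: (169 + 253)/2 = 211 and (253 + 365)/2 = 309. All 3 are reproduced.
- Laboratory, weeks 16 to 32: the first five windows are reproduced.

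**Step 2: try to reproduce the end of the laboratory column.**

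| Laboratory visits assumed | Windows by the midpoint calculation |
|---|---|
| Week 36, then 52 | 239–308, 309–378 |
| Weeks 36, 40, 44, 52 | 239–266, 267–294, 295–336, 337–378 |
| Weeks 36, 40, 44, 48, 52 | 239–266, 267–294, 295–322, 323–350, 351–378 |
| Weeks 34, 38, 42, 52 (Table 1-3 marks taken at their apparent column positions) | 225–252, 253–280, 281–329, 330–378 |
| SAP as written | 239–266, 267–378 |

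None gives 267–378. The fourth reading also fails on earlier windows: it gives 113–140 where the SAP has 127–154. Since 239–266 and 267–378 abut, no window can have been lost between them.

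**Step 3: count.** Table 1-3 shows nine marks, one of them at week 52, so eight come earlier. The SAP has six laboratory windows before day 267. With one sample per window, at least 8 − 6 = 2 scheduled pre-week-52 panels fall in 267–378.

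**Step 4: size of the mislabelling.**

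- Width: 378 − 267 + 1 = 112 days; the five preceding windows are 28 days each.
- Days 267–308, which is 42 of the 112 (37.5%), are closer to day 253 than to day 365.
- Distance from day 365: week 44, 365 − 309 = 56 days; week 40, 365 − 281 = 84 days; the extreme, 365 − 267 = 98 days.
- A week 52 sample taken on days 360–370 is always closest to day 365, so it displaces the earlier panels.

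**The case against.** **No midpoint rule is stated, and other windows are wide.** This is true. The SAP states only that there are no gaps and that the closest visit is used. Weight, modified Mayo, endoscopy and Geboes score have a single window from end of induction + 1 to day 378. A reader might infer that every other long-term window is a midpoint window; the documents do not support that. But those assessments have only one post-induction window, so there is no neighbouring visit to split from, and the first windows of other columns differ only in where they open. Neither case explains an interior boundary at 266/267 followed by 112 days.

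**The schedule is inferred.** This stands. Visit weeks are not visible, and the marks in Table 1-3 do not line up reliably across rows, so the count of nine is supporting evidence rather than proof. A reader might take laboratory visits at weeks 40 and 44 as established; they are plausible, not shown. The conflict with the other columns does not depend on the count.

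**Early-termination visits.** Protocol Sections 4.1.1 and 4.1.2 ask subjects who leave the study to complete week 52 procedures, so the value in the last row may often be an early-termination panel rather than a routine one. That changes which panel is shown, but not the label. Appendix B assigns by study day and gives no separate rule for these visits, so one at day 270 would count as week 52 while one at day 260 would not.

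**Frequency and content.** SAP Section 11 reports that the third interim analysis led to termination for futility. A reader might infer that relabelled panels will be common, but no document says how many subjects left after day 266 without a week 52 sample. Nor does Section 9.6.2 name liver enzymes or blood counts among the selected tests.

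**Conclusion.** The final laboratory window is inconsistent with the rest of Appendix B and appears to conflict with Protocol Table 1-3. Followed as written, it omits scheduled panels after about day 267 when a week 52 sample exists; otherwise it reports the latest panel, including an early-termination panel, as week 52 although taken up to 98 days early.

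The reach is narrow. It is confined to the descriptive by-visit laboratory summaries in SAP Section 9.6.2. The worst on-study shift tables and the worst post-baseline eosinophil table do not depend on nominal visits, and no efficacy analysis uses these laboratory windows. It would be wrong to read this as loss of late safety signals from the report as a whole.

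The window boundaries and the 112-day width are read directly from the SAP. The intervening visit weeks, and hence the 56- and 84-day figures, rest on day = 7 × week + 1 and on the inferred schedule. The number of subjects affected cannot be obtained from the documents.

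**What to change.** Reconcile the laboratory column of Appendix B with the unredacted Table 1-3. Give one window per scheduled laboratory visit, with boundaries midway between adjacent target days:

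- visits at weeks 40, 44 and 52: 267–294, 295–336 and 337–378;
- week 48 also scheduled: 267–294, 295–322, 323–350 and 351–378;
- no visit between weeks 36 and 52: 239–308 and 309–378.

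The cost is a correction to one column of one SAP table and to the program that assigns visits, followed by a rerun of the by-visit laboratory tables. No new data are needed.

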**5.2 Study Points of Reference**

**Baseline:**

Baseline fecal calprotectin is the last measurement taken on or before the date of the first dose of IP.

Baseline for all other parameters is the last measurement for the endpoint of interest taken before the first dose of IP. If the measurement is taken on the same day as the first dose and the exact measurement time relative to the first dose is unknown, it will be assumed to have been taken prior to the first dose of IP.

If a subject did not receive IP, baseline is the closest recorded measurement on or prior to the randomization date for all parameters.

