**Study Day 1:**

Study day 1 for each subject is the first day of IP administration or the day of randomization for subjects who did not receive IP.

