**Study Day:**

Study day for each subject is defined as (day of interest - study day 1) + 1 for dates on or after study day 1, or (day of interest - study day 1) for dates prior to study day 1.

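### SAP Appendix B lets the day 1 pre-dose (baseline) vital signs fill the first post-dose window and displace a reading taken on study day 2

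*SAP*

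**What the plan says.** In the vital-signs column of SAP Appendix B, the first row is "6 to 24 hour Post Dose", with target day 1 and study days 1 to 2. The next is "48 to 96 hour Post Dose", with target day 3 and study days 3 to 5. Within a window, "the visit closest to the target day with non-missing data will be considered for analysis". Ties are handled separately: "If two actual visit dates are at the same distance from the target day, the latest visit with non-missing data will be considered for analysis".

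SAP Section 5.2 supplies the clock and the reference value. "Study day 1 for each subject is the first day of IP administration", and study days are whole calendar days with no hour component. For vital signs, "Baseline for all other parameters is the last measurement for the endpoint of interest taken before the first dose of IP".

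Protocol Table 1-1 schedules vital signs before dosing at the randomization visit, then 6 to 24 hours and 48 to 96 hours after the dose. Protocol Section 6.4.1.1 places randomization on day 1, and a Table 1-1 footnote puts dosing-visit assessments ahead of dosing unless noted otherwise.

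SAP Section 9.6.3 says what is reported: "The actual value, change and percent change from baseline in vital signs will be summarized over time by treatment arm".

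**The concern.** The first vital-sign window has to include study day 1, because a reading 6 hours after a morning dose falls on the dosing day. The same day also holds the pre-dose reading. With distance measured in whole days from a target of day 1, the pre-dose record always sits at distance 0, and a next-day post-dose reading sits at distance 1. The selection rule therefore prefers the wrong record.

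At stake is the first scheduled look at vital signs after first exposure. Protocol Section 2.3 names cardiovascular and respiratory effects and cytokine release syndrome among the potential risks. The error runs one way, toward no change, in a dose-finding study that shows vital signs by arm.

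**Working it through.** The plan gives no figure to reproduce, so the check applies the written rule to the two possible timings.

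**Inputs**
- Window: study days 1 to 2, target day 1 (SAP Appendix B).
- Selection: smallest distance |study day - target day|, with ties going to the latest (SAP Appendix B).
- Baseline: last value before first dose (SAP Section 5.2).
- Illustrative heart rates, assumed: 72 bpm pre-dose and 90 bpm post-dose, a true change of +18.

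**Selection**

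| Post-dose reading on | Pre-dose distance | Post-dose distance | Record selected | Change |
|---|---|---|---|---|
| study day 1 | \|1 - 1\| = 0 | \|1 - 1\| = 0 | post-dose, by the tie rule | 90 - 72 = +18 |
| study day 2 | \|1 - 1\| = 0 | \|2 - 1\| = 1 | pre-dose | 72 - 72 = 0 |

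If candidates are limited to records after the first dose, both rows give +18. The first row is right only if clock time breaks the tie, because the tie rule speaks of visit dates.

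**Comparison with the other columns.** Every other readable first window in Appendix B starts at day 2: chemistry and hematology, urinalysis, fecal calprotectin and hsCRP, antibody, partial Mayo and PGA, lymphocyte subset, and the weight, modified Mayo, endoscopy and Geboes group. That start keeps day 1 baseline records out. The vital-signs column starts at day 1 and has no substitute safeguard.

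**Dilution.** Let f be the share of subjects with the pre-dose reading on study day 1 and the post-dose reading on study day 2. They contribute 0 and the rest contribute their true change. If the effect does not depend on reading time, reported mean = (1 - f) × true mean. For an assumed true mean of +8 bpm:
- f = 25%: 0.75 × 8 = +6 bpm
- f = 50%: 0.50 × 8 = +4 bpm
- f = 75%: 0.25 × 8 = +2 bpm

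**Plausible range for f.** The documents give neither dosing times nor reading times. Suppose readings were uniform over 6 to 24 hours and every pre-dose reading was on the dosing day (both assumed). For a dose at clock hour h, the share on day 2 is (24 - max(6, 24 - h)) / 18:
- 08:00: (24 - 16) / 18 = 44%
- 12:00: (24 - 12) / 18 = 67%
- 16:00: (24 - 8) / 18 = 89%

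These show that f need not be small; they do not estimate it.

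**The case against.** The strongest reply is that the intent is clear. The visit is named as post-dose, Appendix B aims to match each evaluation to its most suitable nominal visit, and SAP Section 5.4 defines change for a post-baseline value. A careful programmer might filter out pre-dose records unasked. This shows intent but does not alter which record the written rule selects. Even if Section 5.4 were used to suppress the zero change, the pre-dose reading would still appear as the value at this visit, and the day 2 reading would still be lost.

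Second, the source text is imperfect. Most visit labels and target days in Appendix B are not legible in the public copy, and Table 1-1 is broken, so the pre-dose placement is read from damaged columns. The two vital-sign rows that matter are legible. A separate baseline row or note in the full table would resolve the point; none is visible.

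Third, not every day 2 reading is lost. SAP Section 5.1 allows first dose and randomization to fall on different dates. A pre-dose reading dated before the dosing day has a negative study day and lies outside the window. A missing pre-dose value also causes no error. It would be wrong to infer that only same-day readings are handled correctly.

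Fourth, a reader might infer that any acute dose-related effect would be hidden. The documents do not support that. The 48 to 96 hour window is untouched. Hypersensitivity, tachyarrhythmia, tachypnea and cytokine release syndrome are found through MedDRA or sponsor queries on adverse events (SAP Section 9.6.1), not from windowed vital signs. Clinically significant vital-sign changes also enter as adverse events (Protocol Section 3). SAP Section 11 records that the study had already met futility and been terminated, and no decision rule in the plan uses this table.

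**Conclusion.** The point holds as a defect in a written rule, with limited reach. When the pre-dose reading is on study day 1 and the 6 to 24 hour reading is on study day 2, Appendix B as written reports the baseline record as the post-dose value and discards the real one. The mean change at that time point is attenuated, not abolished, unless every subject is affected. The factor is about (1 - f) in each arm, where f is that arm's share; f is unknown, and the formula assumes that the effect does not vary with reading time. The consequence is confined to one time point of a descriptive vital-sign summary. It should be corrected because it biases an early safety display toward no change and is cheap to correct; it gives no ground to doubt the efficacy or adverse event results.

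**What to change.** Add to SAP Appendix B that the baseline record, and any record taken before the first dose, cannot fill a post-baseline window. Assign the 6 to 24 hour and 48 to 96 hour vital signs by their nominal collection time point, using clock time since dose only where it was recorded.

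Nominal assignment is safer than windows defined purely in hours. Protocol Section 8.4.1 does not list a reading time among the items to record. SAP Section 5.2 expects some dosing-day readings to have unknown timing and treats those as pre-dose.

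The cost is one SAP sentence and a program filter.
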